4.1. Data Monitoring Committee (DMC)

There will be no DMC for this study.

4.2. Interim Analysis

There will be no interim analysis for this study.

4.3. Final Analysis

All final, planned analyses identified in this SAP will be performed by IQVIA Biostatistics following Sponsor Authorization of this Statistical Analysis Plan, Database Lock and Sponsor Authorization of Analysis Sets.

5. Analysis Populations

5.1. Safety Population

The safety population will consist of all subjects who have taken any study medication. Safety population will be used for all analyses except efficacy analyses.

5.2. Modified Intent-to-Treat [mITT] Population

The modified intent-to-treat (mITT) population will include subjects who are in the safety population and have paper seizure data available. The mITT population will be used for efficacy analyses.

5.3. Per Protocol [PP] Population

The per protocol (PP) population will include subjects who are in the mITT population and did not have any important protocol deviations (IPDs). The per-protocol population will be used in an additional analysis of the efficacy endpoints and subject demographics and baseline characteristics. If no IPDs occurred, as determined by the review team before the database lock, analyses of PP population specified in the SAP will not be performed.

6. General Considerations

6.1. General Principles

Unless stated otherwise, all continuous variables, including those assessed on a discrete scale, will be summarized using descriptive statistics, including number of subjects, mean, standard deviation, minimum, 25th percentile, median, 75th percentile, and maximum. For categorical variables, summaries will include numbers of subjects and percentages.

All endpoints will be summarized descriptively for Arm 1 and Arm 2 separately. There will be no statistical comparisons between Arm 1 and Arm 2.

6.2. Reference Start Date and Study Day

Study Day will be calculated from the reference start date and will be used to show start/ stop day of assessments and events.

Reference start date is defined as the day of the first dose of study medication, (Day 1 is the day of the first dose of study medication) and will appear in every listing where an assessment date or event date appears.

If the date of the event is on or after the reference date then:

Study Day = (date of event – reference date) + 1

If the date of the event is prior to the reference date then:

Study Day = (date of event – reference date)

In the situation where the event date is partial or missing, Study Day, and any corresponding durations will appear partial or missing in the listings.

6.3. Baseline

For the seizure-related endpoints, baseline will be defined as the seizure data for the longest available period up to 3 months prior to screening from seizure history and from screening to first dose of study medication from the paper seizure diary.

Hence, the period of baseline will be calculated as the days of (1 month, 2 months or 3 months) + the number of days from Screening to the first dose from paper seizure dairy. One month will be calculated as 30.42 days.

For all other endpoints, baseline will be defined as the last non-missing measurement taken prior to the first dose of study drug.

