8. SELECTION OF SUBJECTS

8.1. Subject Inclusion Criteria

The subjects who fulfill the following criteria will be included in the study.

1. Male or female subjects \geq 18 years of age.
2. Subject is willing and able to sign informed consent.
3. Subject has a documented diagnosis of epilepsy with simple POS with a motor component or complex POS with or without secondarily generalized seizures as defined in the Classification of Seizures of the International League Against Epilepsy (ILAE, 1981).
4. Subject has a documented electroencephalogram within 10 years prior to screening.
5. Subject has had at least 3 POS during previous six months.
6. Subject has had a sufficient number of seizures at time of enrollment to justify adjunctive therapy, as determined by the Investigator.
7. Subjects are required to be ESL-naïve AND
 - a. Maintained on a stable LEV or LTG regimen for at least 1 month (28 days) prior to screening with no history of adjunctive treatment (for Arm 1, ESL as first add-on).

OR
 - b. Maintained on a stable dose of 1-2 AEDs (excluding OXC) for at least 1 month (28 days) prior to screening and who have had prior adjunctive treatment (for Arm 2, ESL as later add-on).
8. If the subject is treated with any stimulation device for epilepsy (Vagal Nerve Stimulation [VNS], Responsive Neurostimulator [RNS], or similar), the device must have been implanted at least 6 months before screening and the device parameters must be documented as stable for at least 1 month prior to screening. (Note: these devices will not be counted as concomitant AED).
9. Except for epilepsy, subject is judged to be in general good health based on medical history, physical examination findings, and clinical laboratory test results.

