11.2.2.2. Pre-Human Epilepsy Project Instrument

At screening, subjects will complete the HEP. The caregiver may contribute to the HEP data. The HEP instrument is a form administered by an Investigator to obtain a retrospective seizure history, in as accurate a manner as possible, in the absence of a retrospective seizure diary. These data will be used for seizure history only.

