15.3.6. Efficacy Analyses

All efficacy endpoints will be summarized descriptively in this study. Changes in efficacy parameters will be calculated with reference to the baseline, defined as the seizure data for the longest available period up to 3 months prior to screening from seizure history and from screening to first dose of study medication from the paper seizure diary.

All seizure related endpoints will be calculated based on the data from the paper diary.

Seizure frequency will be standardized to 28-day rate. The SSF and changes from baseline will be summarized during the first 12 weeks, the last 12 weeks, and the 24 weeks of the Maintenance Phase.

Two responder rates (50%, and 75% responder rates) are defined as subjects who have $\geq 50\%$, and subjects who have $\geq 75\%$ reduction in SSF from baseline, respectively. The proportions of

responders in each rate will be summarized during the first 12 weeks, the last 12 weeks, and the 24 weeks of the Maintenance Phase.

Relative reduction (%) in SSF from baseline will be calculated during the first 12 weeks, the last 12 weeks, and the 24 weeks of the Maintenance Phase.

The proportion (%) of seizure-free subjects will be provided during the first 12 weeks, the last 12 weeks, and the 24 weeks of the Maintenance Phase.

Time on ESL will be calculated from the first dose to the last known dose of ESL. The median time and 95% CI will be estimated using Kaplan Meier time to event methods. Subjects who were still on ESL at the end of study will be censored at the end of study. Subjects who dropped out of the study while receiving treatment will be an event at the time of the dropout. Change in dosage levels during the treatment period will be ignored.

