3.1. General Description

This is a 31-week, multicenter, 2-arm, prospective, open-label, non-randomized, Phase 4 study of ESL as adjunctive therapy in adult subjects with a diagnosis of epilepsy with POS. Two groups of ESL-naïve subjects will be evaluated. The groups are defined as follows:

Arm 1 (ESL as first add-on): This group will include subjects who have been maintained on a regimen consisting of a stable dose of LEV or LTG for at least 1 month (28 days) prior to screening and who have not used any adjunctive treatment.

Arm 2 (ESL as later add-on): This group will include subjects who have been maintained on a regimen consisting of a stable dose of 1 - 2 anti-epileptic drugs (AEDs) (excluding oxcarbazepine [OXC]) for at least 1 month (28 days) prior to screening and who have used adjunctive treatment in the past.

The Arm 1 subjects will allow an assessment of the efficacy and safety of ESL in subjects who are early in the course of their disease and being treated with one of the most common first line AEDs. The subjects in Arm 2 are similar to the subject population in the Phase 3 adjunctive studies, treatment-resistant subjects who are later in the course of their disease. The inclusion of these subjects in the present study will provide an assessment of the efficacy and safety of ESL as a later adjunctive therapy in a real world clinical setting. In addition, this study will provide data from both Arm 1 and Arm 2 for several behavioral, mood-related, and QOL-related assessments that were not evaluated in the Phase 3 program.

Approximately 100 subjects will be enrolled (approximately 50 subjects in Arm 1 and 50 subjects in Arm 2).

The study will consist of a Screening Phase of 1 to 2 weeks, followed by a 2-week Titration Phase, a 24-week Maintenance Phase, and a Safety Follow-up/Taper Phase of 4 weeks. The last visit in the Maintenance Phase (Visit 9) is considered the End of Study (EOS) visit.

The screening visit should take place 7 - 10 days prior to the titration visit and may be extended to 7 - 17 days if required with consent of medical monitor. Subjects of Asian ancestry who require HLA-B*1502 testing (eg do not have prior test results) may have the screening visit 7 - 17 days prior to the titration visit.

Subjects who withdraw prior to the EOS visit should have an Early Discontinuation Visit (EDV) within 72 hours.

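### Baseline seizure frequency is mostly recalled history while on-treatment frequency is diary only, and the SAP text describes no summary that separates the two sources

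*SAP*

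**What the plan says.** **Baseline.** SAP 6.3 takes "baseline will be defined as the seizure data for the longest available period up to 3 months prior to screening from seizure history" and joins to it the data "from screening to first dose of study medication from the paper seizure diary". The history may cover 1, 2 or 3 months, and "One month will be calculated as 30.42 days". Protocol 15.3 and 15.3.6 define the baseline in the same way.

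**Source of the history.** Protocol 11.2.2.3 derives it from the HEP form. Protocol 11.2.2.2 describes a form that the Investigator administers to reconstruct past seizures "in the absence of a retrospective seizure diary", with caregiver input allowed.

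**Length of the diary part.** Screening normally falls 7 to 10 days before the titration visit, and SAP 3.1 adds that it "may be extended to 7 - 17 days if required with consent of medical monitor".

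**On treatment.** Protocol 11.2.2.4 and SAP 15.2.1 use the paper diary. Protocol 15.3.6 puts it more broadly: "All seizure related endpoints will be calculated based on the data from the paper diary".

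**SSF formula.** SAP 15.2.1 gives one formula for all periods, baseline included. Its numerator is seizures reported in the diary and its denominator is the days in the period.

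**Eligibility.** Protocol 8.1 requires at least 3 partial-onset seizures in the previous six months (criterion 5) and, in the Investigator's judgement, "Subject has had a sufficient number of seizures at time of enrollment to justify adjunctive therapy" (criterion 6).

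**Outputs.** SAP 15.2.2.2 and 15.2.2.4 summarize the pooled baseline, titration, visit intervals, both 12-week halves and the 24 weeks. Neither lists the screening diary or the history on its own. SAP 6.1 and 6.6 exclude arm comparisons and tests.

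**The concern.** Each seizure-reduction endpoint is a within-subject, before-after comparison with no control. The main counting method changes from interview to daily diary between the baseline and the treated period. If the two methods count differently, the difference appears as a change from baseline. Eligibility also depends on past seizures, and the recalled months lie inside the six-month qualifying window, so some regression to the mean is expected.

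The screening diary is the only pre-dose seizure record made with the on-treatment instrument. Pooled with the history, it is a small part of the baseline, and a gap between the two sources cannot be seen in the summaries described. What is at stake is how to read the efficacy results that serve the first secondary objective. The primary retention endpoint is not involved.

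**Working it through.** **Inputs**
- Days per month: 30.42 (SAP 6.3), so 1, 2 or 3 months are 30.42, 60.84 or 91.26 days. This agrees with 365/12 = 30.417.
- Diary days before dosing: 7 to 17 (SAP 3.1).
- Subjects per arm: about 50 (SAP 3.3).
- Recall factor f = recalled rate / diary rate. The documents do not give it; it is assumed and shown as a range.

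**Step 1. Recall share of baseline days**, w = 30.42m / (30.42m + d)

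| History | d = 7 | d = 17 |
|---|---|---|
| 3 months | 91.26/98.26 = 92.9% | 91.26/108.26 = 84.3% |
| 2 months | 60.84/67.84 = 89.7% | 60.84/77.84 = 78.2% |
| 1 month | 30.42/37.42 = 81.3% | 30.42/47.42 = 64.2% |

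The on-treatment share is 0%.

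**Step 2. Apparent change with no drug effect.** In expected rates, the baseline is w·f + (1 − w) times the true rate, so the apparent change is 1/(w·f + 1 − w) − 1. Example for 3 months + 7 days and f = 1.25: 1/(0.929 × 1.25 + 0.071) − 1 = 1/1.232 − 1 = −18.8%.

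| f (assumed) | 3 months + 7 days | 3 months + 17 days | 1 month + 17 days |
|---|---|---|---|
| 0.75 | +30.2% | +26.7% | +19.1% |
| 1.25 | −18.8% | −17.4% | −13.8% |
| 1.50 | −31.7% | −29.7% | −24.3% |

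In expected rates, an unchanged subject reaches a 50% reduction when f = 1 + 1/w, which is 2.08 to 2.19 with 3 months of history. Smaller errors move the responder rate through count variation.

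**Step 3. Responder rate with no drug effect.** Assumptions: Poisson counts, a fixed common rate, 3 months of recall + 10 diary days, 168 treated days.

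| Seizures per 28 days | f = 1 | f = 1.25 |
|---|---|---|
| 1 | about 15% | about 22% |
| 2 | about 7% | about 13% |
| 4 | about 2% | about 6% |
| 8 | about 0.1% | about 1.3% |

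The effect depends strongly on the seizure rate, so no single figure describes it.

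**Step 4. Selection alone (f = 1).** A no-drug simulation used gamma between-subject rates (CV 1, mean 1 to 4 per 28 days), entry on at least 3 seizures in six months, a 3-month + 10-day baseline and 24 weeks of follow-up. The ratio of arm-mean on-treatment SSF to arm-mean baseline SSF was 0.96 to 1.00 with stable subject rates, and 0.87 to 0.97 with a within-subject CV of 1 between periods. Criterion 6 was not modelled.

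**Step 5. Precision of a diary-only check.** At 50 subjects and 2 seizures per 28 days, the diary yields 50 × 7 × 2/28 = 25 to 50 × 17 × 2/28 = 61 seizures, and 3 months of recall yields 50 × 91.26 × 2/28 = 326.
- d = 7: SE of the log ratio = √(1/25 + 1/326) = 0.208, so the 95% CI is ×/÷ exp(1.96 × 0.208) = 1.50.
- d = 17: √(1/61 + 1/326) = 0.140, so ×/÷ 1.32.

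Overdispersion widens both. For one subject at 3 seizures per six months, the chance of an empty diary is 0.89 (7 days) to 0.76 (17 days).

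**Step 6. The SSF formula read literally.** Diary seizures alone over history plus diary days gives d/(30.42m + d) of the true rate: 7/98.26 = 7% to 17/47.42 = 36%. An unchanged subject would then show an increase of 1304% to 179%. This is the opposite direction to over-recall, and larger than any recall error considered above.

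**The case against.** **The baseline is prespecified, in the same way in both documents, and the endpoints are descriptive.** True. That settles which figure is reported. It does not make recall and diary counts comparable, and the figure will still be presented as a reduction from baseline.

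**Terminology is standardized.** Protocol 11.2.2.1 and 11.2.2.4 use the DISCOVER form so that history and diary describe seizures in the same terms. This should reduce misclassification. It does not address forgotten or over-counted events.

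**A reader might infer that the design favours ESL.** The documents do not support this. They give neither the sign nor the size of recall error, and under-recall works against ESL. Only regression to the mean has an expected direction, and it is small unless seizure rates fluctuate.

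**A reader might infer that the screening diary is a clean control, recorded after subjects were selected.** This is not shown. The protocol defines an enrolled subject as one entered into titration (Table 4), and at Visit 2 the site both reviews eligibility again and reviews the diary (Protocol 11.5.2). The diary may itself be partly selected.

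**A reader might infer that no output could reveal a gap.** SAP 15.2.2 promises listings, and SAP 8 refers to templates that are not among the documents reviewed. What can be said is that the SAP text describes no separate summary.

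**A reader might infer that the HEP data are barred from the baseline**, because Protocol 11.2.2.2 says "These data will be used for seizure history only". But Protocol 15.3 explicitly builds the baseline from seizure history, so the restriction does not exclude this use. The paper-diary sentence in Protocol 15.3.6 does sit awkwardly beside the baseline definition in the same section.

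**The check is imprecise.** This stands. At 50 per arm a true ratio of 1.25 lies within the half-interval of a 10-day diary (×/÷ 1.41), so the estimate is too coarse to correct the treatment effect.

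**Conclusion.** The concern holds as a problem of comparability and reporting, not as a demonstrated bias in favour of ESL. Between 64% and 93% of baseline days rest on recall and none of the treated days do; this follows directly from the documents. If recall differs from the diary by 25%, a 3-month-history subject with no true change shows about −17% to −19% (over-recall) or +27% to +30% (under-recall). These sizes rest on assumed recall errors and expected rates. Selection adds a further shift that is small under stable rates and larger if rates fluctuate.

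The SSF change, percent change and responder rates are affected. Retention, time on ESL and on-treatment seizure-freedom do not use this baseline. Separately, the baseline numerator in SAP 15.2.1 does not match its denominator and needs correcting whatever view is taken of recall.

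**What to change.** 1. **SAP 15.2.1:** state that for baseline the SSF numerator is recalled plus screening-diary seizures, to match the history-plus-diary denominator. Do this first, because the size of every percent change depends on it.
2. **SAP 15.2.2.2 and 15.2.2.4:** keep the pooled baseline as primary. Add, by arm, history-only SSF, screening-diary-only SSF, and the diary/recall rate ratio (total seizures over total days) with a subject-level bootstrap 95% CI. Add a supportive arm-level ratio of the on-treatment rate to the screening-diary rate.
3. **Interpretation:** state that change from baseline cannot be separated from recall-versus-diary differences and regression to the mean. Do not subtract the pre-dose difference from the reported effect.

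**Cost:** one or two extra tables from data already collected. The diary-only rate is imprecise (ratio CI about ×/÷ 1.3 to 1.5 at 50 per arm and 2 seizures per 28 days, wider with overdispersion), suits arm-level use only, and should carry a note that it may be partly subject to selection at Visit 2.

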6.4. Retests, Unscheduled Visits and Early Discontinuation Visit (EDV)

In general, for by-visit summaries, data recorded at the nominal visit will be presented including visit 9 (EOS) and EDV. Unscheduled measurements collected prior to the first dose of study medication will contribute to the derivation of the baseline value.

Unscheduled measurements collected post baseline will not be included in by-visit summaries but will contribute to the potentially clinically significant values for vital signs and labs and best/worst case value where required (e.g. shift table).

In the case of a retest (same visit number assigned), the latest available measurement for that visit will be used for by-visit summaries.

Listings will include scheduled, unscheduled, retest and early discontinuation data.

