20. APPENDIX I. CLINICAL LABORATORY TESTS

Clinical Safety Panel

HEMATOLOGY: (Differential reported as % and absolute value)

Hemoglobin, Hematocrit, Platelet Count, Red Blood Cell Count, WBC - Total Count, WBC Differential, (Basophils, Eosinophils, Lymphocytes, Monocytes, Neutrophils)

BLOOD CHEMISTRIES: Alanine aminotransferase (ALT), Alkaline Phosphatase (ALP), Aspartate aminotransferase (AST), Bicarbonate (HCO₃), Bilirubin (Total, Direct, Indirect), Blood Urea Nitrogen (BUN), Calcium (Ca), Chloride (Cl), Creatinine, Glucose, Magnesium (Mg), Phosphorus (P), Potassium (K), Protein (Total), Sodium (Na), Uric Acid, Albumin

URINALYSIS: Blood, Glucose, Ketones, Leukocyte esterase, Microscopic examination, Nitrites, pH, Protein

THYROID PANEL: Free T3, Free T4, TSH

RENAL FUNCTIONING: Creatinine clearance (calculated glomerular filtration rate using the Cockcroft-Gault equation) at Screening only.

URINE DRUG SCREENING: Amphetamines, Barbiturates, Benzodiazepines, Cocaine, Methamphetamines, Methadone, Methylenedioxymethamphetamine (MDMA), Phencyclidine (PCP), Opiates, Oxycodone

OTHER TESTS: Serum Pregnancy (β -hCG) in female subjects of childbearing potential, only; Urine Pregnancy Test (in female subjects of childbearing potential only, on-site testing)

Laboratory reports will be initialed and dated on all pages by the Investigator listed on the Form FDA 1572 (MD or DO). Laboratory test results will be reviewed by the Investigator as they become available. The Investigator must determine the clinical significance of all out-of-range lab values (except drug screens). Possibly drug-related or clinically relevant abnormal values of uncertain causality must be repeated. Any abnormal values that persist should be followed at the discretion of the Investigator.

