6.5. Windowing Conventions

No visit windowing will be performed for this study.

Refer to Appendix 1 for the visit convention for this study.

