16.2. Laboratory Evaluations

Results from the central laboratory will be included in the reporting of this study for Hematology, Blood Chemistry, Urinalysis, Thyroid Panel, Renal Functioning, Urine Drug Screening, Serum Pregnancy and Urine Pregnancy Test. A list of laboratory assessments to be included in the outputs is included in Appendix 1 of the protocol, Section 20.

All laboratory summaries will be used on the safety population and presentations will use SI Units.

Quantitative laboratory measurements reported as "< X", will be converted to X for the purpose of quantitative summaries, but will be presented as recorded, i.e. as "< X" or "> X" in the listings. The following summaries and listings will be provided for laboratory data:

- For laboratory parameters with continuous outcomes (e.g. blood chemistry, hematology, urinalysis data, thyroid panel), descriptive statistics for the actual values and for changes from baseline will be presented by arm for each evaluation time point.
- For laboratory parameters with categorical outcomes (e.g. urinalysis data), the number and percentage of subjects with each outcome will be presented by arm at each evaluation time point.
- Overall summary of the post-baseline PCS will be presented. The number and percentage of subjects with PCS criteria will be summarized by arm . This summary will be also

presented by age group, race group, gender, baseline AEDs and number of baseline AEDs.

- Shifts from baseline by arm for each evaluation time point will be produced to show the percentage of subjects with laboratory test values below, within, and above the normal range.
- Data listing of all clinical laboratory measurements (hematology, blood chemistry, urinalysis, thyroid, and renal function) will be provided. Results outside of the reference range will be flagged.
- Listing of clinically significant out of range laboratory measurements, urine drug screen and serum pregnancy test results will be provided.
- A listing of PCS laboratory findings (e.g. blood chemistry, hematology, urinalysis data, and thyroid function) will be presented for all laboratory parameters with PCS criteria defined in Appendix 3.

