16.2.1. Blood Sodium Levels

In addition to descriptive summaries of blood sodium levels and changes from baseline for each assessment time point, the number and percentage of subjects with normal baseline sodium level (i.e. >135 mEq/L) reaching ≤ 135 mEq/L but > 130 mEq/L, ≤ 130 mEq/L but > 125 mEq/L, ≤ 125 mEq/L, and > 10 mEq/L reduction (ie, < -10 mEq/L) from baseline will be summarized by arm for each evaluation time point and overall post-baseline.

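### When a laboratory repeat carries the Visit 9 or EDV number, the latest-value rule selectively replaces abnormal end-of-treatment results in the by-visit tables

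*SAP*

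**What the plan says.** SAP 6.4 has one rule for each kind of extra measurement.

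- **Retest under the same visit number:** "In the case of a retest (same visit number assigned), the latest available measurement for that visit will be used for by-visit summaries."
- **Unscheduled post-baseline value:** it "will not be included in by-visit summaries but will contribute to the potentially clinically significant values for vital signs and labs" and to best/worst-case values, with the shift table as the example.
- **Listings:** "Listings will include scheduled, unscheduled, retest and early discontinuation data."

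SAP 6.5 adds: "No visit windowing will be performed for this study."

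The laboratory tables that use these rules are in SAP 16.2 ("Shifts from baseline by arm for each evaluation time point will be produced") and SAP 16.2.1, where the sodium categories "will be summarized by arm for each evaluation time point and overall post-baseline."

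The protocol says when a test is repeated, but in two ways. Appendix I: "Possibly drug-related or clinically relevant abnormal values of uncertain causality must be repeated." Section 12.2 makes a repeat of the same class of values optional. Section 12.2 also has clinically significant abnormalities found after dosing or at EOS/EDV recorded as adverse events and followed until the test is normal or stable.

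The schedule of assessments places the laboratory and thyroid panels at screening and at Visit 9 or the EDV only.

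**The concern.** A latest-value rule is harmless when repeats are unrelated to the result. Here the described reason for a post-baseline repeat is an abnormal result, and neither document calls for repeating a normal one. Choosing the latest value then selects on outcome: a low sodium that is repeated and has risen leaves the by-visit table, while a normal value that would have been low on a second draw is never replaced.

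Three features of this trial make that matter more than usual:

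- The exposed value is the subject's only scheduled post-dose laboratory result, so no earlier on-treatment visit preserves the finding.
- Neither document limits how late a retest may be. Subjects who withdraw early come off ESL, so a later draw can reflect recovery.
- The SAP does not say whether a superseded first value still counts in the PCS, shift and overall post-baseline sodium summaries. Two programmers could produce different tables from the same text, and tables in one report could disagree.

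At stake is how faithfully the by-visit laboratory tables describe end-of-treatment values, including the sodium categories that the plan singles out.

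**Working it through.** The plan gives no figure for this effect, so there is nothing to reproduce. Retest frequency, timing and coding are also not given. They are assumptions below.

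**1. Which value reaches the table.** Take an abnormal Visit 9 sodium and one later repeat.

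| Repeat filed as | By-visit table uses | First value in PCS and overall post-baseline summaries |
|---|---|---|
| Visit 9 retest | the repeat | not stated |
| Unscheduled | the first value | counts as the scheduled value; the repeat also counts |

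The same blood draw is handled in opposite ways according to its label. For shifts, SAP 6.4 names a best/worst-case use, while SAP 16.2 plans them at each time point.

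**2. Effect at the threshold that prompts the repeat.** Let p be the share abnormal by first value, r the share of those repeated under the same visit number, and q the share of those repeats that are normal. With no repeats of normal values, the by-visit share becomes p(1 − r·q). For an assumed p = 10%:

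- r = 0: 10%
- r = 0.25, q = 0.25: 10% × (1 − 0.0625) = 9.4%
- r = 0.5, q = 0.5: 10% × (1 − 0.25) = 7.5%
- r = 1, q = 0.75: 10% × (1 − 0.75) = 2.5%

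With about 50 subjects per arm (SAP 3.3), 10% is 5 subjects. The middle case removes 5 × 0.25 = 1.25 of them, and the last removes 5 × 0.75 = 3.75.

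**3. Sodium at or below 135 mEq/L, simulated.** Assumed: on-treatment mean 138, between-subject SD 2.5, within-subject SD 1.5 or 2.0, repeats prompted at 135 or below. By first value the share is 15.1% to 17.5%.

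| Recovery at repeat | Share repeated | At or below 135, latest value | Rise in mean, mEq/L |
|---|---|---|---|
| none | 25% | 13.4% to 15.2% | 0.05 to 0.08 |
| none | all | 8.3% to 8.4% | 0.18 to 0.32 |
| 2 mEq/L | 25% | 12.2% to 14.0% | 0.12 to 0.17 |
| 2 mEq/L | all | 3.3% to 3.8% | 0.48 to 0.67 |

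The rows with no recovery show that regression to the mean alone produces the effect. No taper is needed.

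**4. Single sodium bands.** Second simulation, assumed: usual sodium mean 140, SD 1.5; fall on drug gamma-distributed (shape 2, mean 3); within-person SD 1.5; every triggered value repeated while still on drug. By first value, 2.0% are at or below 130 and 23.1% at or below 135, so 21.2% lie between (unrounded, 23.14% − 1.96%).

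| Repeat prompted at | At or below 130 | At or below 135 | Above 130, up to 135 |
|---|---|---|---|
| 130 | 1.1% | 23.1% | 22.0% |
| 132 | 1.6% | 22.7% | 21.1% |
| 135 | 1.9% | 15.1% | 13.2% |

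The share beyond the trigger falls each time. Other bands need not: with a trigger at 135 the share at or below 130 hardly moves, and with a trigger at 130 the band above it rises from 21.2% to 22.0%. Both simulations ignore the restriction to subjects with normal baseline sodium.

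**5. Who could be repeated off drug.** At the assumed completion rates of 60% and 50%, 40% of Arm 1 and 50% of Arm 2 withdraw early and come off ESL. If 20% of completers also stop (assumed), the shares are 0.40 + 0.60 × 0.20 = 52% and 0.50 + 0.50 × 0.20 = 60%. These are shares of subjects, not of repeats. The number of repeats taken after dose reduction or stopping cannot be derived.

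**The case against.** The rule is conditional. It needs the same visit number, and the protocol allows unscheduled visits at any time. Laboratory work is central, so a repeat prompted by a result will normally need a later draw. If sites file that draw as unscheduled, the first value stays in the by-visit table. The later the draw, the less likely it is to carry the Visit 9 or EDV number. This stands, and it is why the size is unknown.

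A reader might infer that abnormal results are often replaced by values from during or after the taper. The documents do not support this: they give no frequency or timing of repeats, and completers who continue commercial ESL have no taper. A reader might also infer that every sodium category improves. Step 4 shows otherwise. Nor does the protocol uniformly require repeats: Appendix I and section 12.2 disagree, and both cover only possibly drug-related or clinically relevant abnormal values of uncertain causality.

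It is also fair that nothing disappears from the record. Listings carry original and repeat values, clinically significant out-of-range results have their own listing, and clinically significant abnormalities enter the adverse event tables. No primary or efficacy result is touched.

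Two warnings about remedies stand as well. Limiting the tables to on-treatment samples could drop scheduled EDV samples, because the EDV may come up to 72 hours after withdrawal and ESL may be stopped abruptly for an adverse event. Setting the worst post-baseline value against a last-value baseline would inflate by-visit shifts towards abnormal.

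What the objection does not remove is that the SAP provides for same-visit retests and, for them, chooses the value in a way that depends on the first result.

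**Conclusion.** The concern holds in a limited form. When a repeat carries the Visit 9 or EDV number, SAP 6.4 replaces abnormal end-of-treatment laboratory values selectively. By-visit means, changes and the share beyond the repeat threshold then tend to look more favourable, possibly through values taken after ESL was reduced or stopped.

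The direction at the triggering threshold follows from the text, given that repeats are prompted only by abnormal values. The size does not. It runs from nothing (no same-visit repeats) to most of the abnormal share (all repeated, most normal on repeat). The simulated figures are illustrations on assumed sodium distributions.

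Separately, the SAP leaves open whether a superseded value counts in the PCS, shift and overall post-baseline sodium summaries. That gap needs no assumption.

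The consequence is confined to descriptive safety tables in an uncontrolled study without statistical testing. It is worth correcting because the remedy is cheap and these are the only scheduled post-dose laboratory data.

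**What to change.** Amend SAP 6.4 for laboratory data, along these lines:

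- Post-baseline by-visit summaries, including by-visit shifts and sodium categories, use the first valid measurement at the scheduled visit. The scheduled EDV sample is included whether or not ESL has already been stopped.
- A retest replaces that value only if the first sample was invalid (for example haemolysed).
- Original and repeat values, whether filed as retest or unscheduled, all count in the PCS and overall post-baseline (worst-case) summaries.
- Values taken after the last ESL dose are flagged.
- Baseline stays the last non-missing value before the first dose.

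Align the shift-table example in SAP 6.4 with the by-time-point shifts in SAP 16.2. The repeat instructions in Protocol Appendix I and section 12.2 must be reconciled with each other.

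The cost is one SAP paragraph and a programming flag before database lock. Abnormal counts may be slightly less favourable and may include some spurious single values. If screening tests were repeated, the baseline will still lean slightly towards normal relative to a first post-baseline value. That asymmetry is smaller than under a worst-value rule and can be noted in the report.
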